1.3.5. Efficacy, Parameters

A summary of these endpoints outlining the Analysis Set (population), age limitations, details of the pre-specified baseline, and other pertinent details is found in Table 3.

The primary efficacy endpoint is the proportion of patients (\geq 12 years of age) who achieve a \geq 10% reduction from baseline in body weight after \sim 52 weeks of treatment in the Full Analysis Set (FAS) population.

[figure not shown]
The following 3 endpoints have been identified as key secondary efficacy endpoints.

- Mean percent change from baseline in body weight (in patients ≥12 years of age after ~52 weeks of treatment in the FAS population.
- Mean percent change from baseline in the weekly average of the daily hunger score (in patients \geq 12 years of age) after \sim 52 weeks of treatment in the FAS population.
- The proportion of patients who achieve a ≥25% improvement in the weekly average of the daily hunger score (in patients ≥12 years of age) after ~52 weeks of treatment, in the FAS population.

18

Other secondary endpoints include:

- Mean percent change from baseline in body weight (in patients ≥12 years of age) at the Week 14 visit after treatment with setmelanotide as compared with placebo in the ~14 Week Placebo-controlled Analysis Set (PCS) population.
- Mean percent change from baseline in the weekly average of the daily hunger score (in patients ≥12 years of age) at the Week 14 visit after treatment with setmelanotide as compared with placebo in the PCS population.

Rhythm Pharmaceuticals, Inc. Statistical Analysis Plan, Protocol RM-493-023 29 October 2020, Version 3.0

2. ANALYSIS POPULATION

2.1. Population Definitions

The following analysis populations will be evaluated and used for presentation and analysis of the data.

- Screening Analysis Set: All patients who signed the informed consent form.
- Safety Analysis (SA) Set: All patients who received at least 1 dose of study drug (placebo or setmelanotide). Analysis performed on the safety set will be based on patients according to treatment received.
- FAS: All patients (irrespective of age) who received at least 1 dose of setmelanotide and have baseline data.
- DUS: All patients in the FAS who demonstrate at least 5 kg weight loss (or at least 5% if baseline body weight is < 100 kg) over the first 14 weeks of active setmelanotide treatment, regardless of later disposition.

For any DUS analysis, the DUS subgroup includes:

- O Those patients initially randomized into the setmelanotide group in the double blinded, randomized, placebo-controlled period that achieved at least 5 kg weight loss (or at least 5% if baseline body weight is < 100 kg) from baseline at Week 15 visit.
- O Those patients who initially randomized in the placebo group in the double blinded, randomized, placebo-controlled period, and achieved at least 5 kg weight loss (or at least 5% if baseline body weight is < 100 kg) from week 15 (i.e., just prior to their first active dose of setmelanotide at week 15) through week 29 (i.e., after 14 weeks of active treatment with setmelanotide).
- PCS: All randomized patients who received at least 1 dose of placebo or setmelanotide and have baseline data. This population is specifically defined for the 14-week placebo-controlled, double-blind period (Period 1). Analysis performed on PCS will be based on subjects as randomized.
- Per-Protocol Set at End of Period 1 (PP at EOP1): All subjects in PCS without any major protocol violations that will result in exclusion of the subjects from the analysis.
- Per-Protocol Set at End of Period 2 (PP at EOP2): All subjects in FAS without any major protocol violations that will result in exclusion of the subjects from the analysis.
- Completers Set (CS): all subjects in the PP at EOP1 population who continue on active treatment or placebo to complete a full 14-week placebo-controlled double blinded period (Period 1)

The FAS population is the primary population for the analysis of efficacy endpoints. The DUS population may be used for sensitivity analyses of efficacy endpoints, as appropriate.

The SA Set is the primary population for the analysis of safety endpoints.

The following analysis sets may be used for supportive/exploratory analyses (note that in the following exploratory analysis sets, if a patient's height at the primary endpoint timepoint,

i.e., ~Week 53 visit, is not available, then the last available measurement of height will be used to define the analysis sets).

[figure not shown]

2.2. Protocol Violations

At the discretion of the Sponsor, major protocol violations, as determined by a review of the data prior to unblinding of the study results and the conduct of statistical analyses, may result in the removal of a subject's data from the PP Set. The Sponsor or designee will be responsible for producing the final protocol violation file (formatted as a Microsoft Excel file), in collaboration with the data monitoring group (or designee) as applicable; this file will include a description each protocol violation and clearly identify whether or not this violation warrants exclusion from the PP Set. This file will be finalized prior to database lock. An analysis performed on the PP set may be provided only if the number of patients in the PP set is 20% less than that in FAS/PCS set.

All protocol violations will be presented in a data listing.

3. GENERAL STATISTICAL METHODS

3.2. General Methods

All data listings that contain an evaluation date will contain a relative study day (Rel Day). Pre-treatment and on-treatment study days are numbered relative to the day of the first dose of study medication which is designated as Day 1. The preceding day is Day -1, the day before that is Day -2, etc.

All output will be sorted and labeled according to the International Conference on Harmonization recommendations and formatted to the appropriate page size(s).

Tabulations will be produced for appropriate demographic, baseline, efficacy, and safety parameters. For categorical variables, summary tabulations of the number and percentage of subjects within each category of the parameter will be presented. For continuous variables, the number of subjects (N), mean, 95% confidence interval of the mean, median, standard deviation (SD), minimum, and maximum values will be presented.

Formal statistical hypothesis testing will be performed on the primary efficacy endpoint with testing conducted at the 1-sided, 2.5% level of significance. Summary statistics will be presented, as well as confidence intervals (CIs), as described in the sections below. Trial success will be based on a 1-sided p-value <0.025.

3.3. Computing Environment

Unless otherwise noted, all descriptive statistical analyses will be performed using SAS® statistical software (SAS Institute Inc., Cary, NC, USA). Medical history and AEs will be coded using the Medical Dictionary for Regulatory Activities (MedDRA). Concomitant medications will be coded using World Health Organization (WHO) Drug Dictionary.

3.4. Baseline Definitions

To assess the dual nature of efficacy parameters, two efficacy baseline definitions will be used.

- Placebo-controlled period baseline (PCPB): is defined as the last available measurement prior to the first dose of setmelanotide or placebo. PCPB will be used for efficacy analysis based upon 14 weeks of treatment with either setmelanotide or placebo.
- Active treatment baseline (ATB): is defined as the last available measurement prior to the first dose of active setmelanotide. ATB will be used for efficacy analyses based upon ~52 weeks of treatment.

For safety, including key laboratory (e.g. hematology and chemistry) parameters, the last measurement prior to the first dose of setmelanotide or placebo will be used as the baseline.

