1.4.3. Mechanism-Related Adverse Experiences of Interest

The most significant safety issue for MC4R agonist compounds in an obese patient population is the potential for mechanism-based increases in BP or HR, which were observed with another MC4R agonist (LY2112688, Eli Lilly and Company) at all doses tested in a clinical study in healthy volunteers.

Setmelanotide was developed with the specific goal to provide equal or greater efficacy as LY2112688 in animal models without producing the cardiovascular side effects observed with LY2112688. Nonclinical studies in obese monkeys showed that setmelanotide did not increase BP or HR, and clinical data suggest that there is little, if any, evidence to suggest that changes from baseline in BP or HR are greater in patients who received setmelanotide compared with those who received placebo, nor is there evidence of pharmacokinetic (PK)/PD relationship between exposure and changes in BP or HR (Gottesdiener 2015).

Other potential safety and/or tolerability issues reported from clinical and/or nonclinical studies with other MC4R agonists in the literature include nausea and vomiting, male penile erections, increases in female sexual arousal, and off-target activity at the closely related MC1R (which mediates melanin production in the skin, producing tanning).

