8.3. Definition of Baseline

Baseline for statistical analyses of data from the double-blind period is defined as the last available measurement prior to the randomization (ie, Day 1), for patients randomized into either the setmelanotide or placebo group.

Baseline for statistical analyses following ~52 weeks setmelanotide treatment is defined as follows:

- For patients initially randomized into the setmelanotide group, baseline is defined as the last available measurement prior to the randomization (ie, Day 1)
- For patients initially randomized into the placebo group, baseline is defined as the last available measurement prior to the first dose of open-label setmelanotide treatment (ie, Week 14 or pre-dose Week 15)

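### Under the SAP's general safety baseline, on-setmelanotide changes in placebo-first patients include any net change left over from 14 weeks of placebo

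*SAP*

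**What the plan says.** SAP 3.4 announces that "two efficacy baseline definitions will be used". The first, PCPB, is the last value before any study drug and serves the 14-week analyses. The second, ATB, is the last value before active setmelanotide, and its use is limited: "ATB will be used for efficacy analyses based upon ~52 weeks of treatment".

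Safety is then handled in one sentence. It opens "For safety, including key laboratory (e.g. hematology and chemistry) parameters" and ends "the last measurement prior to the first dose of setmelanotide or placebo will be used as the baseline". Laboratory values are named as an included example, so the sentence reads as a rule for safety in general.

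Protocol 8.3 also has two definitions, but its second is not confined to efficacy: "Baseline for statistical analyses following ~52 weeks setmelanotide treatment is defined as follows". For patients randomised to placebo it is "the last available measurement prior to the first dose of open-label setmelanotide treatment". SAP 1.1.1 says that the SAP overrides the protocol where they differ, so the single safety baseline governs.

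No other visible text supplies a second safety baseline. SAP 4.2 summarises height, weight and BMI at the start of active treatment, but only as patient characteristics.

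**The concern.** The design has two treatment sequences. Setmelanotide-first patients have one natural baseline, because Day 1 is also their first active dose. Placebo-first patients have two reference points 14 weeks apart. The SAP saw this for efficacy and introduced ATB to deal with it, but did not carry ATB over to safety. A placebo-first patient's change on setmelanotide therefore starts from a value taken before placebo.

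After Period 1 there is no concurrent control, so change from baseline becomes a main way to read measured safety on drug. Protocol 1.4.3 ranks "the potential for mechanism-based increases in BP or HR" as the leading safety question for this drug class. If blood pressure or heart rate settles during placebo, a later on-drug rise in these patients is partly or wholly offset. If it drifts upward, the drift looks like a drug effect. In a shift table, a laboratory value that became abnormal on placebo, and is still abnormal at an on-drug visit, counts as a shift on setmelanotide.

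**Working it through.** **Inputs**
- First dose of study drug on Day 1, first open-label dose on Day 99, end of Period 2 on Day 365 (SAP Table 1).
- About 52 weeks on setmelanotide in placebo-first patients falls at Day 462 (SAP 3.10.1).
- Allocation 1:1 (SAP 1.3.1); pivotal cohort of 38 (SAP 1.1.1). About 38/2 = 19 patients are therefore placebo-first, assuming an even split, which the documents do not report.

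**Reproducing the stated periods**
- Period 1: (99 − 1)/7 = 14.0 weeks.
- Period 2: (365 − 99)/7 = 38.0 weeks.

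Both agree with the plan.

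**Decomposition.** For a placebo-first patient, write Y0 for the pre-Day 1 value, Y15 for the pre-dose Week 15 value and Yt for a later value on setmelanotide.
- SAP safety change: Yt − Y0 = (Y15 − Y0) + (Yt − Y15).
- The first bracket is the net placebo-period change. A change that arose and resolved before Week 15 contributes nothing.
- Change from ATB: Yt − Y15, the second bracket alone.
- For setmelanotide-first patients Y0 is also the ATB value, so nothing alters.

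**Share of the measured interval spent on placebo**
- At Day 365: (365 − 1)/7 = 52.0 weeks, of which 14 on placebo; 98/364 = 27%.
- At Day 462: (462 − 1)/7 = 65.9 weeks, of which 14 on placebo; 98/461 = 21%.
- From ATB the intervals become 38.0 weeks and (462 − 99)/7 = 51.9 weeks, all on setmelanotide.

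**Effect on means.** Let D be the mean of (Y15 − Y0) in placebo-first patients.
- Their own mean on-drug change is displaced by D.
- A mean pooled over both sequences is displaced by 0.5 × D + 0.5 × 0 = D/2.
- The documents give no D. For assumed values in arbitrary units, D = +2 displaces the pooled mean by +1, and D = −5 displaces it by −2.5.

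**What ATB does not remove.** Suppose a drift or regression to the mean, r, acts over the first 14 weeks in both sequences and persists.
- Single baseline: both sequences carry r, so the pooled displacement is 0.5r + 0.5r = r.
- ATB: setmelanotide-first patients still carry r, and placebo-first patients no longer do, so it is 0.5r + 0 = r/2.
- Drift after the first setmelanotide dose stays in both sequences under either baseline.

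**The case against.** The strongest reply is that the affected tables cannot be seen. Protocol 8.6 and the SAP's detailed safety sections are not in the public text, and later pages of SAP Table 3 have a baseline column but no readable rows. No visible passage plans a pooled on-setmelanotide safety change. This stands as a limit: the point concerns the general rule in SAP 3.4, and a reader should not infer that every safety table is affected.

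Second, if safety is tabulated by visit and randomised group, the Week 15 change appears beside later changes, and the on-drug mean follows by subtraction when the data are complete. That is right for means within a sequence. It does not recover a shift table from Week 15, nor the spread of the on-drug change, and it fails once the sequences are pooled.

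Third, the pre-Day 1 baseline is correct for the randomised Week 14 comparison, the only controlled safety evidence. That stands, and the fix leaves it alone.

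Two stronger readings are tempting.
- A reader might turn an assumed D into a rate at which safety intervals falsely exclude zero. The documents do not support this. They give no size for D; SAP 3.2 presents confidence intervals for continuous variables as summary statistics and states no decision rule for safety. Such a rate would also assume that the shift occurs only in placebo-first patients. Drift or regression would act in both sequences, and ATB would not bring the rate back to nominal.
- A reader might suppose that the baseline is a raw first-visit value, with strong regression to follow. The rule takes the last value before dosing, after a screening period of two to three weeks.

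**Conclusion.** The point holds for the rule as written. In placebo-first patients, any measured safety parameter reported as change from baseline on setmelanotide includes the net placebo-period change still present at Week 15. The displacement is D in those patients and about D/2 in a mean over both sequences. Its direction is unknown, so it can overstate or hide an on-drug change.

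This assumes near-equal allocation in the patients analysed, and that no unseen safety section makes an exception. It does not touch adverse-event counts, the Period 1 randomised comparison or any efficacy result. It is a correctable weakness in how measured safety on drug will be read, and it departs without stated reason from the broader wording of Protocol 8.3.

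**What to change.** In SAP 3.4:
- Keep the pre-Day 1 baseline for safety summaries of Period 1.
- Use the existing ATB definition, the last value before the first setmelanotide dose, for change-from-baseline and shift summaries on setmelanotide, in line with Protocol 8.3.
- Keep the pre-study value in the listings.
- If the unseen safety sections already do this, one sentence in 3.4 should say so.

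The cost is wording, an ATB flag extended from efficacy to safety parameters, and a second set of safety change tables. The laboratory and vital-sign rows of the schedule are not visible, so a pre-dose Week 15 value is assumed. Where a patient has none, the definition falls back on an earlier pre-setmelanotide value, and part of the placebo-period change then remains. The tables should also note that ATB does not correct for drift or regression to the mean on drug.

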3.5. Methods of Pooling Data

Data will be pooled across genetic obesity populations (BBS and AS). The primary analysis will be performed based on pooled pivotal patients. Separate tabulations for efficacy parameters may be provided for the two genetic obesity populations, but no formal tests for differences in efficacy between groups will be carried out. BBS is a polygenic disorder; many participants may have "private" mutations different from all others in the study, and disparities in response by genotype are to be anticipated even within the BBS cohort, making formation of subgroups for statistical testing likely impossible.

3.6. Adjustments for Covariates

No formal statistical analyses that adjust for possible covariate effects are planned.

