3.4. Justification of the Study Design

Setmelanotide is being evaluated as a potential treatment for rare, genetically defined obese populations.

Both BBS and AS patients are included in the patient population of this study. While there is significant overlap in the clinical features of these syndromes, there are also some well known differences. However, despite any differences, the mechanism that drives the propensity for the obesity/hyperphagia phenotype is likely the same between the 2 syndromes, abnormal primary ciliary development and impaired leptin receptor signaling arising from BBSome dysfunction in

hypothalamic neurons caused by *BBS* or *ALM1* mutations. Because setmelanotide's mechanism of action in the MC4R pathway is downstream from the leptin receptor, it has the potential to be effective in both diseases.

Confirmation of efficacy will be based on weight loss response after ~52 weeks (1 year) of setmelanotide treatment compared to a historical weight loss rate taken from a large well characterized registry of BSS patients. The 1-year treatment duration was chosen to allow sufficient time for potential weight loss and to ensure that early weight loss is sustained. However, the study will also include a 14-week double-blind, placebo-controlled period in which 50% of patients will receive matching placebo and 50% will receive setmelanotide. Results from this placebo-controlled period will provide an insight into the immediate effect of setmelanotide compared with placebo on early weight loss and the unrelenting hunger/hyperphagia that is characteristic in these diseases. In particular, the effect of setmelanotide on hunger scores should be rapid and the evaluation strengthened by this initial placebo portion of the study. A full year double-blind, placebo-controlled period was not considered because the projected weight loss responder rate of the untreated population is well understood from the CRIBBS registry. Importantly, patient retention would be especially challenging in a full year placebo-controlled trial.

The rationale for using patients \geq 12 years of age at baseline for the primary efficacy analysis is provided in Section 8.5.1.

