Once 10% of patients without a confirmed BBS diagnosis have been enrolled in the study, sites will be notified that only genetically confirmed BBS patients may be enrolled.

- 2. ≥ 6 years of age.
- 3. Obese, defined as BMI \geq 30 kg/m² for patients \geq 16 years of age or weight >97th percentile for age and sex on growth chart assessment for patients 6 to 15 years of age.
- 4. Study participant and/or parent or guardian is able to communicate well with the Investigator, to understand and comply with the requirements of the study, and is able to understand and sign the written informed consent/assent.
- 5. Female participants of child-bearing potential must be confirmed non-pregnant and agree to use contraception as outlined in the protocol. Female participants of non-childbearing potential, defined as: surgically sterile (status post hysterectomy, bilateral oophorectomy, or bilateral tubal ligation), post-menopausal for at least 12 months (and confirmed with a screening follicle stimulating hormone (FSH) level in the post-menopausal lab range), or

- failure to have progressed to Tanner Stage V and/or failure to have achieved menarche, do not require contraception during the study.
- 6. Male participants with female partners of childbearing potential must agree to use a double barrier method contraception if they become sexually active during the study or within 90 days following their participation in the study. Male patients must also not donate sperm during and for 90 days following their participation in the study.

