1. INFORMATION FROM THE STUDY PROTOCOL

1.1. Introduction and Objectives

1.1.1. Introduction

This document presents the statistical analysis plan (SAP) for Study RM-493-023, A Phase 3 trial of Setmelanotide (RM-493), a Melanocortin-4 Receptor (MC4R) Agonist, in Bardet-Biedl Syndrome (BBS) and Alström syndrome (AS) Patients with Moderate to Severe Obesity. This SAP is based upon protocol version dated 26 August 2020.

This SAP is designed to outline the methods to be used in the analysis of study data in order to answer the study objectives. Populations for analysis, data handling rules, statistical methods, and formats for data presentation are provided. The statistical analyses and summary tabulations described in this SAP will provide the basis for the results sections of the clinical study report (CSR) for this study.

In addition, the SAP is intended to clarify many of the details of the more limited discussion in the statistical section of the protocol, therefore, the SAP will expand on and may modify the plans outlined in the study protocol. If changes are made to the plans outlined in the protocol, the SAP will supersede the relevant contents of the protocol. If, after the study has completed, changes are made to the SAP, then these deviations to the plan will be listed, along with an explanation as to why they occurred, in the Clinical Study Report for the study as appropriate. It should be noted that a cohort of the supplemental patients was added into the protocol in the midcourse of the study. However, the sponsor has specified that the patients categorized in the pivotal cohort include all the enrolled BBS/AS patients at the time of the planned sixth AS patient enrollment. Based on this definition, and up to the finalization of the SAP, it is concluded that a total of 38 patients (the first 32 BBS patients and 6 AS patients) will make up the pivotal cohort. The full list of pivotal cohort patients is provided in Appendix I. All analyses for CSR and Submission, including demographics, disposition, baseline characteristics, efficacy, and safety etc., will be performed and the conclusions will be drawn based on the data from the pivotal cohort of patients. The purpose of the supplemental cohort is to gain more treatment experience. Therefore, unless stated otherwise, all analyses in the SAP refer to pivotal cohort only.

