1.3.2. Randomization Methodology

This study will be open label, except for a 14-week double-blind, placebo-controlled period.

Patients who qualify for the study will return to the site on Day 1 of the double-blind period. Prior to randomization, the Investigator will ensure that the patient continues to meet inclusion and exclusion criteria. Patients who continue to be eligible to participate in the study will be assigned a unique randomization number based on a randomization code that will be generated prior to the start of the study. The randomization number codes the patient's initial treatment assignment (for the double-blind period) to either setmelanotide or placebo. The randomization scheme will randomize patients in a 1:1 ratio, stratified by age group (≥12 years or <12 years) and disease (BBS or AS), to receive either setmelanotide or placebo during the first 14 weeks of the study. Randomization numbers will not be re-used once assigned. Please refer to the official randomization plan for greater details.

The Investigator, study site staff, clinical research organization staff providing site management, and Medical Monitor will not have access to the actual treatment assignment administered during the 14-week double-blind, placebo-controlled treatment period (Period 1) except in the case of an emergency until all randomized participants have completed both the 14-week double-blind, placebo-controlled period and the 38-week open-label portion of the study (Period 2).

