3.10.3. Approach on Missing Value in ~14-Week Placebo-Controlled, Double-Blinded Period (Period 1)

Patients may have missing values in Period 1 for many reasons such as drop out, early discontinuation, missed visits, or AEs etc. Missing values in this period will be imputed with a similar MI approach as 52 week analysis as defined in the primary imputation approach.

However, as this analysis revolves around 14 week timepoint, VC3 will be the focus of the imputation model. VC1, VC2, and VC3 will used in the multiple imputation model (SAS PROC MI) for 14 week timepoint with treatment group as a class factor. A sensitivity analysis may be conducted based on treatment failure approach on the missing value imputation for this period as appropriate.

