4.3.3. Other Secondary Efficacy Analyses of the 14-week, placebo-controlled period

These analyses will be performed on patients in the PCS population, (i.e., on data from the ~14-week, placebo-controlled, randomized, double-blinded period, or Period 1). Where applicable, the secondary endpoint will be compared against the null hypothesis for each of the 100 imputed datasets. The outcomes from the 100 imputed datasets will be combined using Rubin's Rule to provide a p-value and corresponding confidence interval as appropriate.

Body Weight Percent Change from Baseline at 14 Weeks:

The analysis on this secondary endpoint will be a between-group comparison to investigate if setmelanotide-treated patients (\geq 12 years old) exhibit a greater decrease in percent change in body weight from baseline at \sim 14 weeks of therapy, as compared to placebo-treated patients.

This analysis will be based on a two-sample t-test for each of the 100 imputed datasets. The outcomes from the 100 imputed datasets will be combined using Rubin's Rule to provide a p-value and corresponding confidence intervals. This will be evaluated at a 1-sided, 0.025 significance level.

Sensitivity analyses based on PP at EOP1 and CS may be provided.

Descriptive statistics for the change and percent change from baseline in body weight (kg) may be presented for the PCS population by visit by randomized treatment.

Daily Hunger Score Percent Change from Baseline at 14 Weeks

The analysis on this secondary endpoint will be a between group comparison to investigate if setmelanotide-treated patients exhibit a greater improvement from baseline at ~14 weeks of therapy in weekly average of daily hunger scores, as compared to placebo-treated patients. This analysis will be based on a two-sample t-test for each of the 100 imputed datasets. The outcomes from the 100 imputed datasets will be combined using Rubin's Rule to provide a p-value and corresponding confidence intervals. This will be evaluated at a 1 sided, 0.025 significance level.

Prior to analysis, daily hunger scores for each of the 3 hunger assessments will be averaged separately by week, as outlined above. Sensitivity analyses based on PP at EOP1 and CS may be provided.

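### The Week-14 placebo comparisons leave out the disease stratum used in randomisation: the t-test stays valid, but loses some power if AS and BBS outcomes differ

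*SAP*

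**What the plan says.** SAP 1.3.2 randomises patients 1:1, "stratified by age group (≥12 years or <12 years) and disease (BBS or AS"). SAP 4.3.3 compares the arms at Week 14 on percent change in weight and in hunger score, one-sided at 0.025. For weight it says "This analysis will be based on a two-sample t-test for each of the 100 imputed datasets", and hunger is handled in the same way. SAP 3.6 adds: "No formal statistical analyses that adjust for possible covariate effects are planned". In SAP 3.10.3 the Week-14 imputation uses the first three visit categories "for 14 week timepoint with treatment group as a class factor"; disease is not named.

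On numbers, SAP 1.1.1 says that "a total of 38 patients (the first 32 BBS patients and 6 AS patients) will make up the pivotal cohort". That count covers all ages, and Protocol 4.2 admits patients "≥ 6 years of age", whereas the Week-14 endpoints are restricted to patients aged 12 or over. The count aged 12 or over, by disease, is not given.

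On whether the diseases differ, Protocol 3.4 holds that "the mechanism that drives the propensity for the obesity/hyperphagia phenotype is likely the same between the 2 syndromes", while SAP 3.5 says "disparities in response by genotype are to be anticipated even within the BBS cohort". SAP 3.8.1 plans Week-14 analyses within each disease and labels their p-values exploratory.

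**The concern.** Stratified allocation balances AS and BBS patients across the arms, which takes AS-BBS variation out of the treatment difference. An unadjusted t-test leaves that variation in the error term. If disease is prognostic, the estimated standard error is then larger than the true one: intervals are too wide, the test rejects too rarely under the null, and power is lost. The age stratum raises no such problem, because it is constant once the analysis is restricted to patients aged 12 or over. Disease is the only randomisation factor that the test ignores.

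This matters because the 52-week primary and key secondary tests are one-sample, so Week 14 supplies the only concurrent-control evidence, and the arms are small. The direction is harmless for false positives. What is at stake is precision on two other secondary endpoints.

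Leaving out baseline weight or hunger is not part of this point. Baseline is not a stratification factor, and omitting it does not make the test conservative.

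**Working it through.** The documents give no sample size, effect size or SD for Week 14, so there is no figure of theirs to reproduce.

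**From the documents:** 1:1 allocation stratified by disease (SAP 1.3.2); one-sided 0.025 (SAP 4.3.3); at most 38 patients, 6 of them AS (SAP 1.1.1).

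**Assumed:** N = 24, 30 or 38 patients aged 12 or over, with 2, 4 or 6 AS; within-disease SD of 1; AS-BBS gap d in SD units; permuted blocks of 2 (exact balance for even counts) or 4, since SAP 1.3.2 leaves the method to a separate randomisation plan; complete data; treatment effects of 1.197, 1.060 and 0.934 SD, which give the t-test 80% power at N = 24, 30 and 38 when d = 0.

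**Analytic check.** Let q be the AS share. Under exact balance, the expected error variance of the t-test, relative to the within-disease variance, is 1 + [N/(N−2)]·q(1−q)·d².

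- N = 38, 2 AS, d = 1: q = 0.0526, so 1 + (38/36)(0.0499) = 1.053. The square root is 1.026, a standard error 2.6% too large.
- N = 24, 6 AS, d = 1: q = 0.25, so 1 + (24/22)(0.1875) = 1.205. The square root is 1.098, about 9.8% too large. Simulation gives 9.9%.

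**Simulation.** 100,000 runs per setting, d = 1, blocks of 2, t-test against a linear model with treatment and disease. Losses are from unrounded powers.

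| N | AS | t-test type I error | Power, t-test | Power, adjusted | Loss (points) |
|---|---|---|---|---|---|
| 24 | 2 | 0.0211 | 77.5% | 79.7% | 2.2 |
| 24 | 4 | 0.0179 | 75.6% | 79.8% | 4.2 |
| 24 | 6 | 0.0159 | 74.0% | 79.7% | 5.7 |
| 30 | 2 | 0.0216 | 77.9% | 79.7% | 1.8 |
| 30 | 4 | 0.0193 | 76.6% | 80.0% | 3.5 |
| 30 | 6 | 0.0169 | 74.9% | 79.7% | 4.8 |
| 38 | 2 | 0.0226 | 78.3% | 79.8% | 1.5 |
| 38 | 4 | 0.0205 | 77.2% | 80.1% | 2.8 |
| 38 | 6 | 0.0185 | 76.1% | 80.0% | 3.9 |

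Type I error of the adjusted model is 0.0246 to 0.0254. A repeat run with a different seed agreed to within about 0.2 point on every loss.

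**Other settings:**

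- *Blocks of 4, 1 SD gap:* type I error 0.018 to 0.025, loss 1.0 to 5.7 points.
- *Simple randomisation, 32 BBS and 6 AS:* t-test type I error stays near 0.025 at gaps of 0, 1 and 2 SD. The conservatism therefore needs balance within disease as well as a gap.
- *0.5 SD gap:* loss 0.3 to 1.3 points under exact balance. With blocks of 4, the adjusted model runs from 0.6 point worse to 1.1 better.
- *No gap:* adjusting costs 0.1 to 0.2 point under exact balance, 0.3 to 0.6 with 3 or 5 AS patients, and up to 1.2 with N = 24, two AS and blocks of 4, where both AS patients can fall in one arm.
- *Diseases differ only in response to drug:* adjusting gains 0.3 to 2.3 points if AS patients get none of the effect, and 0 to 0.3 if they get half.
- *Larger effects, 1 SD gap, blocks of 2* (N = 24 with 4 AS, 30 with 4, 38 with 6): the loss falls to 2.0, 1.6 and 1.8 points with effects 25% larger, and to about half a point with effects 50% larger.
- *Hunger:* patients who cannot rate their own hunger use a caregiver tool, so fewer may be analysed. Assuming 16 or 20 patients with 2 or 4 AS and a 1 SD gap, the loss is 2.7 to 5.9 points under exact balance and about 1.8 to 6 with blocks of 4. With no gap, adjusting costs 0.3 to 0.5 point, and up to 2.2 with two AS and blocks of 4.

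**The case against.** The best defence is that nothing here is an error. The SAP deliberately pools the diseases, declines adjustment and plans separate Week-14 analyses by disease. The protocol's own Week-14 weight test, a rank test, was unadjusted too. The stated rationale is a shared mechanism, and the genotype differences expected within BBS would not be absorbed by an AS/BBS term. The 1 SD gap and 80% power are chosen rather than documented; with a smaller gap or a larger effect the loss shrinks, and in sparse settings adjustment does slightly worse. The Period 1 data probably already exist, so changing the test now carries a cost in credibility.

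Most of this stands, and it is why the point is an optional efficiency gain. It does not remove the point. The by-disease analyses are exploratory and do not replace a stratified overall estimate. The protocol calls the shared mechanism only likely. The section on earlier efficacy by disease (Protocol 1.4.2.1) has no text in the public copy, so a difference not shown here is not a difference ruled out. If every AS patient aged 12 or over fell in one arm, the adjusted model could still be fitted; those patients would simply add nothing to the treatment contrast. The blind is to be kept until the snapshot for the primary analysis, so a blinded amendment remains possible.

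**Conclusion.** The point holds, at low severity and with medium confidence. The Week-14 t-tests are valid and add no false-positive risk. They are conservative only if AS and BBS outcomes differ and allocation is balanced within disease. The first condition is not shown in the documents, and the second depends on a randomisation plan that is not in view.

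Under the assumed 1 SD gap the cost for weight is roughly 1 to 6 points of power. At half that gap it is about 1 point or less, and it can reverse when there are only two AS patients. These figures come from complete data, not from the planned multiple imputation. The case for adjusting is that a usually small cost protects against a somewhat larger possible loss, using a factor the trial already randomises by.

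**What to change.** - **SAP 3.6:** state that no covariate adjustment is planned except for disease stratum (BBS or AS) in the Week-14 between-group comparisons.
- **SAP 4.3.3:** in each imputed dataset, fit a linear model of Week-14 percent change on treatment and disease stratum, pool by Rubin's rules and test one-sided at 0.025. Keep the two-sample t-test as a sensitivity analysis.
- **SAP 3.10.3:** add disease to the Week-14 imputation model where it can be fitted; otherwise leave it out and record that. SAP 3.10.1 already warns that observations may be too few for the regressions.

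If the sponsor prefers the t-test, one sentence in SAP 3.6 saying why the disease stratum is left out would suffice.

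The cost is a dated amendment and a few lines of code. The number of AS patients aged 12 or over can be read without treatment codes, so the choice can be fixed before unblinding. SAP 4.7 expected Period 1 to be complete by about the end of 1Q2020 and SAP version 3.0 is dated 29 October 2020. The amendment should therefore state that its authors had seen neither treatment codes nor any early Period 1 results, which SAP 4.7 withholds until the primary analysis.

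Baseline adjustment is a separate option. On the same assumptions it gains power only if baseline explains more than about 3 to 6% of the variance, and otherwise costs about 1 to 2.5 points.
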